EOS	End of Study
EPI	Exocrine pancreatic insufficiency
ER	Emergency room
GI	Gastrointestinal
HADS	Hospital Anxiety and Depression Scale
HIPAA	Health Insurance Portability and Accountability Act
HRQOL	Health-related quality of life
ICF	Informed consent form
IRB	Institutional review board
LTFU	Lost to follow-up
N/A	Not applicable
OTC	Over the counter

USA

Abbreviations	Term or Definition
PACT-CP	PAtient-CenTric Chronic Pancreatitis Registry
PERT	Pancreatic enzyme replacement therapy
PRO	Participant-reported outcome
PT	Preferred Term
RAP	Recurrent acute pancreatitis
RMP	Registry monitoring plan
SAE	Serious adverse event
SAP	Statistical analysis plan
SD	Standard deviation
SF-12	12-item Short Form Survey
TFL(s)	Tables, Figures and Listings
TSQM-9	Treatment Satisfaction Questionnaire for Medication – 9 items

USA

1 INTRODUCTION

The purpose of this Statistical Analysis Plan (SAP) is to provide detailed descriptions of the statistical methods, data derivations, and data displays for study protocol NES-EPI-100 “PAatient-CenTric Chronic Pancreatitis Registry” version 3.0 (13APR2021). The table of contents and templates for the Tables, Figures and Listings (TFLs) will be produced in a separate document.

All data analyses and generation of TFLs will be performed using SAS® version 9.4 or higher. The SAP will be finalized and signed off prior to locking the database.

USA

2 STUDY OBJECTIVES

2.1 Main Objective

The main objective of this study is to generate real-world evidence reflecting the experience of individuals with exocrine pancreatic insufficiency (EPI) due to chronic pancreatitis (CP). Efforts will be directed toward understanding the unmet need and therapeutic burden to identify the most critical factors that influence treatment choices/prescribing patterns, quality of life, and healthcare utilization outcomes in standard of care for individuals with EPI due to CP. This study has the following specific aims:

1. Create a cohort of well-characterized patients with EPI due to CP for participation in retrospective and prospective research
2. Collect clinical data to characterize both the EPI due to CP disease history and disease progression through a combination of retrospective and prospective collection of medical history, comorbidities, and treatment approaches aimed at increasing the level of understanding of a heterogeneous condition such as EPI
3. Collect data on the differing clinical care practices for patients with EPI to better understand the impact of those patterns on outcomes (including quality of life, comorbidities, and treatments)
4. Collect data on treatment compliance that may impact the EPI due to CP disease experience and/or outcome
5. Collect baseline and longitudinal participant-reported outcome (PRO) data on abdominal pain, GI symptoms, dietary habits, health-related quality of life, depression/anxiety, and PERT use and treatment satisfaction to evaluate the impact of EPI on individuals' health and daily life
6. Gather data on healthcare utilization to be combined with clinical data to generate evidence for the impact and burden of EPI due to CP in this cohort on the healthcare system

USA

3 STUDY DESIGN

3.1 Overall Design

This is a prospective, non-interventional study for individuals with EPI due to CP who are under the care of a gastroenterologist. Longitudinal data will be collected from both study participants as well as from their clinical encounters with their treating gastroenterology providers using a structured and standardized data collection method. The scope of data collection (see [Table 1](#)) from the study participants includes demographics, current work status, current insurance coverage, family disease history, weight/height, current over the counter (OTC) herbal/nutritional supplements, healthcare utilization, and PROs on abdominal pain, GI symptoms, dietary habits, health-related quality of life, depression/anxiety, and PERT use and treatment satisfaction. At the time of routine clinical encounters, Investigators complete assessments on medical history, information on suspected/confirmed EPI diagnosis, CP etiology, clinical manifestations of EPI (GI and nutritional manifestations), AEs, and current treatment(s).

This is a 5-year study with an anticipated first enrollment date of 01 April 2021. The total enrollment period will be 24 months in length and data collection and study close-out will take place 3 months prior to the anticipated study end date. The study duration from enrollment to study end is five (5) years.

Study data will be collected from Investigators at the time of routine clinical encounters, as well as from study participants remotely in between routine visits.

Enrollment

Study participants will be enrolled in the study if they meet eligibility criteria and after they have provided consent to participate. During the Enrollment Visit, the Investigator will confirm eligibility and will provide information on suspected/confirmed EPI diagnosis (date of diagnosis, date of onset of symptoms indicative of EPI, method of EPI diagnosis, if applicable), CP etiology, clinical manifestations of EPI (i.e., GI and nutritional manifestations), medical history (comorbidities, surgical and radiological procedures, endoscopic procedures, and laboratory abnormalities), and current treatment(s). Information collected from the study participant

USA

includes demographics, current work status, current insurance coverage, family disease history, weight/height, current over the counter (OTC) herbal/nutritional supplements, healthcare utilization, and participant-reported outcome assessments on abdominal pain, GI symptoms, health-related quality of life, depression/anxiety, and PERT use and treatment satisfaction.

Follow-Up

Follow-up data will be collected from the study participants remotely via electronic data capture (EDC) portal. Every 3 months, study participants will complete assessments on current work status, current insurance coverage, current weight, current OTC herbal/nutritional supplements, and abdominal pain, GI symptoms, and PERT use and treatment satisfaction. Every 6 months, in addition to the assessments completed every 3 months, study participants will also complete assessments on health-related quality of life, depression/anxiety, and healthcare utilization.

The Investigator will provide updates during routine clinical encounters approximately every 6 months or at least 150 days from the last registry visits. Data will be collected on clinical manifestations of EPI, current treatment(s), and active assessment of adverse events/serious adverse events (AEs/SAEs) since last visit. “Early” follow-up visits will be conducted whenever a study participant is prescribed a new PERT product. The Investigator will not complete any assessments if the study participants do not return to the sites for their expected routine clinical encounter.

Study Participant Exit

Study participants exit the study upon withdrawal from the study, lost to follow-up (LT FU), transfer of care to a different gastroenterologist, death, or any other reason resulting in a study participant’s exit. The Investigator will document the reason for the exit.

3.2 Schedule of Assessments

The registry activities are summarized in the schedule of assessments outlined in [Table 1](#).

USA

3.3 Sample Size

Sample size is determined by the investigators' judgment. Target enrollment is approximately 400 study participants with suspected or confirmed EPI. Approximately 20 clinical gastroenterology sites in the United States will be contracted to participate.

Table 1. Schedule of Assessments

	Enrollment Day 0	Follow-up direct from study participant		Follow-up on-site (Clinical encounter) Every 6 months*	Study participant exit [‡] May occur any time; max. data collection period is 5 years
		± 7 days	Every 3 months		
Study Participant Provided Data[§]					
Informed consent	X				
Demographic information	X				
Family disease history	X				
Training for remote assessment completion	X				
Height	X				
Weight	X	X			
Current Insurance/work status	X	X			
Current OTC nutritional/herbal supplements	X	X			
Abdominal pain	X	X			
GI symptoms	X	X			
PERT use and treatment satisfaction	X	X			
Dietary habits	X		X		
Health-related quality of life	X		X		
Anxiety/depression	X		X		
Healthcare utilization	X		X		

USA

	Enrollment Day 0	Follow-up direct from study participant \pm 7 days		Follow-up on-site (Clinical encounter) Every 6 months*	Study participant exit[‡] May occur any time; max. data collection period is 5 years
		Every 3 months	Every 6 months		
Investigator Provided Data*					
Review/confirm participant eligibility	X				
EPI diagnosis	X				
CP etiology	X				
Medical history	X				
EPI clinical manifestations	X			X	
AEs [•]				X	
Current treatment(s)	X			X	
Reason for exit					X

§ Study participant provided data will be collected remotely via EDC portal.

* Investigator provided data will be provided during clinical encounters at the registry site. Every 180 days \pm 30 days with minimum 150 days between visits unless follow-up visit meets criteria for EARLY On-Site Follow-Up (see section 6.3.2)

[‡] Occurs if data collection period has ended or if study participant exits the study due to death, is LTFU, transfers to another gastroenterologist, withdraws from the study or being terminated by the Investigator.

[•] The Investigator will provide information about the occurrence and seriousness of AEs at Follow-up. In the event that an AE is serious, the Investigator will complete an SAE form.

USA

4 STUDY POPULATION

4.1 Screened Population

The screened population will consist of enrolled patients who fill the informed consent form.

4.2 Enrolled Population

The enrolled population will consist of enrolled patients who both fill the informed consent form and meet eligibility criteria.

USA

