The prevalence of EPI in the general population is unknown. It is most often associated with diseases of the exocrine pancreas, being a common late-stage manifestation of CP. CP is a disorder characterized by ongoing pathological pancreatic inflammation, leading to fibrosis and eventually to the loss of both endocrine and exocrine function. EPI typically develops after 5 – 10 years of CP, requiring approximately 90% of the endogenous pancreatic enzyme secretion to be lost (C. E. Forsmark, 2013). The risk of EPI varies with the underlying etiology of CP, with the highest risk population being those with chronic alcohol use (Ammann et al., 1987). Smoking has an independent effect on the development of CP, and the probability of EPI increases when tobacco exposure is combined with alcohol (Luaces-Regueira et al., 2014). In addition, EPI can also occur following severe acute pancreatitis (AP) as a result of loss of pancreatic parenchyma and functional capacity due to significant amounts of pancreatic necrosis (Hollemans et al., 2018), or recurrent acute pancreatitis without the overt presence of CP at the time of evaluation. Other causes for EPI are pancreatic malignancies (Sikkens et al., 2014) and resective pancreatic surgeries such as pancreatic duodenectomy (Goess et al., 2016) and distal pancreatectomy (Okano et al., 2016). EPI is also observed in other conditions, such as cystic fibrosis (Singh & Schwarzenberg, 2017), diabetes (Mohapatra et al., 2016), inflammatory bowel disease (Maconi et al., 2008), and GI surgeries (Antonini et al., 2018; Huddy et al., 2013; Straatman et al., 2017).

The diagnosis of EPI is best made by a combination of clinical history, ruling out other causes of malabsorption, cross sectional imaging of the pancreas, and diagnostic tests. The most practical approach involves diagnostic procedures that are noninvasive, inexpensive, and readily available. Such available lab tests are indirect measures of pancreatic function and include fecal elastase-1 (FE-1) test, fecal fat measurement, and fat-soluble vitamin measurements. These tests are generally less expensive and easier to perform compared to direct pancreatic functional tests.

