5.2 Inclusion Criteria

To be eligible for enrollment, a study participant must meet the inclusion criteria below:

1. At least 18 years of age (or age of majority)
2. Willing to provide consent to participate
3. Meet ONE (1) of the following at the time of enrollment:
 - a. Diagnosis of chronic pancreatitis (CP)
 - b. Diagnosis of recurrent acute pancreatitis (RAP)
4. Suspected or confirmed diagnosis of EPI made by a healthcare provider
5. On PERT, either prior to the Enrollment Visit or newly prescribed at the time of the Enrollment Visit.

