11. DATA ANALYSIS

Statistical analyses will be guided by the specific aims of the registry. Complete details of all analyses will be described in a standalone Statistical Analysis Plan (SAP) with accompanying mock Tables, Figures and Listings (TFLs).

All data will be summarized descriptively. Continuous variables will be described through reporting of the mean (\pm standard deviation), median and range, while categorical data will be described through reporting of frequency and percent. The participant population will be characterized by demographics and baseline attributes. From this characterization, important subgroups of interest may be identified if sample sizes are sufficiently robust for additional exploratory analyses. All pre-planned, clinically important subgroups for analyses will be identified in the SAP.

Study disposition of all participants will be summarized including dropouts (with reasons presented for those who drop out), and for lost to follow-up (at what point they are lost, and if they return).

Multivariate modeling will be employed to study both the EPI due to CP disease history and disease progression by analyzing patterns of medical history, comorbidities, and treatment approaches. Variables in the modeling will also include clinical care practices and their impact on the modeling.

Clinical care practices will be further explored with their potential impact on quality of life, comorbidities, and treatments using the same multivariate modeling. Treatment compliance will be examined for each of the models, knowing that biases are introduced with participant recall. Prescribing practices will be descriptively presented (to include type of PERT, dose at initiation and escalation, recommendation on how to take PERT, and reason for switching to another PERT, if applicable). If trends are identified in prescribing patterns, these trends may be further explored.

Healthcare utilization data will be assessed with key variables from the clinical dataset. Impact and burden of EPI due to CP will be assessed for impact on the healthcare system (the number of ER visits, healthcare provider visits, number of hospitalizations, length of hospital stay, and number of sick days taken). Associations will be presented descriptively, and if the data are robust, inferential statistics will be presented using rates and 95% confidence intervals.

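### The SAP addresses EPI due to CP using a CP-or-RAP cohort with no count or display by qualifying diagnosis, and has no rule for Day-0 PERT ratings entered before any PERT was taken

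*SAP*

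**What the plan says.** **Population.** The main objective (SAP 2.1) concerns the experience of people with EPI due to CP (its wording is "individuals with exocrine pancreatic insufficiency (EPI) due to chronic pancreatitis (CP"). SAP 5.13 on healthcare utilization and SAP 5.15 on modeling are framed in the same terms. Protocol 5.2, criterion 3, requires only one of two diagnoses: CP, or the second option ("Diagnosis of recurrent acute pancreatitis (RAP"). The protocol background treats the two as separable, since it says EPI can arise with "recurrent acute pancreatitis without the overt presence of CP at the time of evaluation". SAP section 4 defines a screened set and an enrolled set, the latter as "The enrolled population will consist of enrolled patients who both fill the informed consent form and meet eligibility criteria". SAP 5.3 presents baseline data for all enrolled participants.

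**Day-0 PERT ratings.** Protocol 5.2, criterion 5, admits anyone "On PERT, either prior to the Enrollment Visit or newly prescribed at the time of the Enrollment Visit". SAP Table 1 marks "PERT use and treatment satisfaction" at Enrollment Day 0 with no exception, and SAP 5.3 counts it among the baseline characteristics. SAP 5.5 summarizes how enzymes have affected symptoms, on five ratings from greatly improved to greatly worsened. SAP 5.5.1 summarizes the TSQM-9 by subscale and gives rules only for a missing item.

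**Not available for this review.** SAP section 1 says of the display shells: "The table of contents and templates for the Tables, Figures and Listings (TFLs) will be produced in a separate document". The data-entry forms were not provided either.

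**The concern.** A plan that asks about EPI due to CP but summarizes CP and RAP-only participants together answers a slightly different question. If the qualifying diagnosis is never tabulated, a reader cannot tell how different. Anyone using the utilization or modeling results as evidence on EPI due to CP would be relying on a mixture of unknown composition.

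The second matter is validity of a rating. Someone prescribed PERT for the first time at the Enrollment Visit has no experience of it to rate. If such a person fills in the TSQM-9 or the impact item anyway, the answer enters the baseline summary as if it described treatment. The impact item is also a potential dependent variable in SAP 5.15, where PERT type and dose at initiation are potential predictors, so the same answers could reach the models.

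**Working it through.** There is no plan figure to reproduce. The target of about 400 is set by judgment (SAP 3.3), and no RAP-only share, new-starter share or Day-0 completion rate is given. The check is therefore mainly textual.

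**Does anything in the SAP text separate CP from RAP-only?**
- The etiology table in SAP 5.3 includes a class for recurrent and severe acute pancreatitis. That classifies the cause of CP, not the diagnosis that qualified the participant.
- SAP 5.6 tabulates medical history by term, and SAP 5.15 lists medical history as a candidate predictor. Neither is a CP/RAP split.
- SAP 5.15 allows stratified analysis if confounding is found, without naming this factor.
- Protocol 11 leaves pre-planned, clinically important subgroups to the SAP. The SAP text names none.

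**Does anything screen out ratings given before PERT was taken?**
- Blank forms drop out: SAP 5.1 summarizes non-missing values and imputes nothing. The gap concerns ratings that are entered.
- SAP 5.5 says *if applicable* without defining it, and 5.5.1 does not repeat it.
- SAP 5.5 lists a not-applicable category for dose escalation, and 5.14 does so for COVID-19 items. None is listed for the impact item.
- Day 0 is the consent date (SAP 5.1). Protocol 8.3 has enrollment forms completed at the site, while the Table 1 footnote says participant data are collected remotely. Whether a rating precedes the first dose is therefore not settled.

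**Illustration 1: mixing and the cost of a CP display.** Assume a RAP-only share r of 400.
- CP n = 400 × (1 − r)
- 95% half-width for a 50% proportion = 1.96 × √(0.25/n)
- Full-cohort mean minus CP mean = r × (RAP-only mean minus CP mean), so a 3-point shift needs a group difference of 3/r. Three points is the change that SAP 5.11 calls meaningful for the SF-12, used here only as a yardstick.

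| r (assumed) | CP n | Half-width, points | Group difference for a 3-point shift |
|---|---|---|---|
| 0% | 400 | 4.9 | – |
| 10% | 360 | 5.2 | 3/0.10 = 30 |
| 20% | 320 | 5.5 | 3/0.20 = 15 |
| 40% | 240 | 6.3 | 3/0.40 = 7.5 |

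**Illustration 2: exposure of Day-0 ratings.** Assume that a share s of 400 had taken no PERT before the rating, that a fraction of them leave the form blank, and that everyone else completes it. The table gives affected ratings as a share of all ratings entered.

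| s (assumed) | All blank | Half blank | None blank |
|---|---|---|---|
| 5% (20 people) | 0/380 = 0% | 10/390 = 2.6% | 20/400 = 5% |
| 10% (40 people) | 0/360 = 0% | 20/380 = 5.3% | 40/400 = 10% |
| 20% (80 people) | 0/320 = 0% | 40/360 = 11.1% | 80/400 = 20% |

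These figures bound how many records could be affected. They do not estimate bias, since the documents give no group difference.

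**The case against.** The strongest reply is that the mixed cohort is deliberate and openly stated. RAP is in the eligibility criteria, SAP 3.3 describes the target as participants with suspected or confirmed EPI, and sections 5.13 and 5.15 use the CP phrase when stating purpose. No table title has been seen. The analysis is descriptive and exploratory, with no error rate or power at stake. This stands as a limit on severity. It does not remove the mismatch between the question posed and the population analysed, or the missing count.

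A reader might infer that the SAP breaches the protocol by omitting a CP subgroup. The documents do not support that. Protocol 11 says "important subgroups of interest may be identified if sample sizes are sufficiently robust for additional exploratory analyses", and although it sends pre-planned subgroups to the SAP, it does not say that CP versus RAP is one of them.

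On the ratings, the reply is that the form may skip these items for people not yet on PERT, and that *if applicable* may be meant to cover the impact item. Either could be so; neither is written down.

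Three stronger readings also fail:
- **Every newly prescribed participant's Day-0 rating is invalid.** Newly prescribed is not the same as never having taken PERT. A former user could rate it validly, and a form completed remotely could follow the first dose.
- **TSQM-9 change from baseline is distorted.** The shift tables in SAP 5.1 are for categorical variables and are themselves conditional. SAP 5.5.1 plans only descriptive statistics by subscale and listings. Only the impact item could reach a shift table.
- **Symptom-change tables must be split by PERT status.** Nothing in the gap described here requires that.

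**Conclusion.** Both points hold, for the SAP text only. The SAP addresses EPI due to CP with a cohort that may include RAP-only participants, and it plans neither a count by qualifying diagnosis nor a CP-only display. It also lets TSQM-9 and PERT-impact ratings entered before any PERT was taken into the baseline summaries. For the impact item alone, such ratings could also enter a shift table, if one is produced, and the 5.15 models.

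The effect cannot be sized and its direction is unknown. With few RAP-only participants, only a very large group difference would matter; with many, a modest one could. The conclusion assumes that neither the unseen table shells nor the form logic already deals with these points. Priority is low to moderate.

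**What to change.** **Population.** In SAP section 4, derive CP (with or without RAP) versus RAP-only from enrollment data, and report the counts with the baseline characteristics in 5.3. Show the 5.13 and 5.15 results for CP-diagnosed participants beside the full enrolled cohort. At minimum, label full-cohort results as EPI due to CP or RAP.

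**Day-0 ratings.** In SAP 5.5 and 5.5.1, state that a TSQM-9 or PERT-impact rating is not applicable when the participant had taken no PERT before giving it. Base the rule on actual prior intake, not on newly prescribed status. Use the first on-treatment assessment as that participant's first value, and footnote the later timing.

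**Cost.** If the database holds the qualifying diagnosis and prior PERT intake, this is SAP and table-shell wording, to be settled before database lock. Table 1 lists only an eligibility confirmation, so if either item is not stored, a form change or a one-off site query is needed. The CP display has a smaller n, at the modest precision cost shown in the first table; relabelling alone avoids that. People who had not yet taken PERT would have a first TSQM-9 value about 3 months later, at the next scheduled assessment. If the shells or forms already handle either point, a sentence in the SAP saying so is enough.
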